9.4.9. Serum Creatinine and eGFR

Serum creatinine measurements are not reliable with concurrent dialysis. Therefore, all serum creatinine values obtained while a patient is on dialysis will be excluded from all analyses. Estimated Glomerular Filtration Rate (eGFR) will be imputed with a value of 10 (in mL/min/1.73 m²) while a patient is on dialysis. A patient will be considered on dialysis from the first day of dialysis through 5 days after the end of dialysis.

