15.12. Other Statistical Issues

15.12.1. Missing or Invalid Data

If a Day 1 assessment is missing, the Screening assessment will be used as the baseline assessment.

For evaluation of Complete TMA Response during the 26-week Initial Evaluation Period (primary endpoint), patients missing an efficacy assessment that is part of the definition of Complete TMA Response while still on-study, will have their last observation carried forward (LOCF). For patients who will have terminated early from the study prior to Week 26, their data up to the time of discontinuation will be used to assess Complete TMA Response.

Missing data for QoL instruments will be handled as specified in the instructions for each instrument.

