5. DEFINITIONS

5.1. Efficacy

5.1.1. Primary Endpoint(s)

The primary efficacy endpoint of the study is Complete TMA Response during the 26 week Initial Evaluation Period. The criteria for Complete TMA Response are the following:

1. Normalization of platelet count (defined as platelet count $\geq 150,000$ per microliter)
2. Normalization of LDH (defined as LDH \leq upper limit of normal)
3. $\geq 25\%$ improvement in serum creatinine from baseline

Patients must meet all Complete TMA Response criteria at 2 separate assessments obtained at least 4 weeks (28 days) apart, and any measurement in between.

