7.2.1. Primary Analysis

The primary efficacy endpoint is Complete TMA Response during the 26-week Initial Evaluation Period. The primary analysis will consist in estimating the proportion of complete TMA responders among ALXN1210 treated patients. This will be performed by calculating the point estimate and a 2-sided 95% confidence interval (CI) for the proportion of complete TMA responders in ALXN1210 treated patients, where the numerator will be the number of patients achieving complete TMA response during the 26-week Initial Evaluation Period and the denominator will be the number of patients in the FAS. The CI will be based on the asymptotic Gaussian approximation method with a continuity correction.

The criteria for Complete TMA response are presented in [Section 5.1.1](#). Patients must meet all Complete TMA Response criteria at 2 separate assessments obtained at least 4 weeks (28 days) apart, and any measurement in between. To be considered a responder during the 26-week Initial Evaluation Period, the latest time point a patient can first meet the response criteria is 28 days before the Day 183 assessment.

Formal statistical comparison analyses are not planned for this estimation study. Results from ALXN1210 treated patients will be evaluated in the context of results observed in patients treated with eculizumab in prospective eculizumab studies.

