7.2.1.1. Handling of Dropouts or Missing Data

For evaluation of Complete TMA Response during the 26-week Initial Evaluation Period (primary endpoint), patients missing an efficacy assessment that is part of the definition of Complete TMA Response while still on-study, will have their last observation carried forward (LOCF). For patients who will have discontinued from the study prior to Week 26, their data up to the time of discontinuation will be used to assess Complete TMA Response. A confirmatory result cannot be from an assessment that was carried forward from the initial assessment when all Complete TMA Response criteria were met.

For laboratory data, in the event of duplicate samples from local and central laboratories (for any time point), central laboratory results will be used for analysis.

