9.4.3. Change from Baseline

Change from baseline will be calculated as the baseline value subtracted from the value at a particular time point. If one of the values is missing and there are no pre-specified missing value imputation rules (see [Section 7.2.1.1](#)), then a change from baseline will not be calculated.

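### No rule scores an on-dialysis visit as failing the creatinine criterion, so a patient dialysed between two qualifying visits is a confirmed responder whether the excluded value is carried forward or ignored

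*SAP*

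**What the plan says.** - **Endpoint.** SAP 5.1.1 requires a platelet count of at least 150,000 per microliter, LDH no higher than the upper limit of normal, and creatinine at least 25% better than its baseline value. It adds a persistence rule: "Patients must meet all Complete TMA Response criteria at 2 separate assessments obtained at least 4 weeks (28 days) apart, and any measurement in between". SAP 7.2.1 adds that "the latest time point a patient can first meet the response criteria is 28 days before the Day 183 assessment".
- **Dialysis.** Under SAP 9.4.9 "all serum creatinine values obtained while a patient is on dialysis will be excluded from all analyses". The on-dialysis period runs from the first day of dialysis until 5 days after it ends. Over those days eGFR is set to 10, and SAP 9.4.11 places dialysis in CKD stage 5.
- **Missing components.** Protocol 15.12.1 prescribes LOCF for "patients missing an efficacy assessment that is part of the definition of Complete TMA Response while still on-study". SAP 7.2.1.1 repeats the rule and adds one guard: "A confirmatory result cannot be from an assessment that was carried forward from the initial assessment" at which all criteria were met.
- **Change from baseline.** SAP 9.4.3 sets the condition "If one of the values is missing and there are no pre-specified missing value imputation rules" and gives as its consequence "then a change from baseline will not be calculated". It refers to 7.2.1.1 for such rules.
- **Dialysis-based response.** SAP 7.2.2.3 has a modified definition that replaces the creatinine criterion with coming off dialysis. It is not the primary definition and covers only patients on dialysis at baseline.

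**The concern.** The exclusion in 9.4.9 removes a value that the primary endpoint needs, and nothing says what happens next. The SAP does not state whether an excluded creatinine counts as missing (so that LOCF fills it), as no measurement, or as a failed visit. Two programmers could follow the SAP and classify the same patient differently. A confirmed renal response could also span a visit that the same SAP stages as kidney failure.

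The situation is foreseeable. Protocol 8.1 (criterion 2c) admits patients who need dialysis for acute kidney injury. Protocol 9.7 restricts new dialysis only in the first 48 hours. SAP 7.2.2.1 summarises post-baseline dialysis even among patients not on dialysis at baseline.

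This is the primary proportion of a single-arm estimation study that SAP 7.2.1 reads in the context of eculizumab results. Time to response and response over time use the same definition and inherit the gap. The sensitivity analysis in SAP 7.2.1.5 uses the per protocol set, which does not remove patients dialysed after 48 hours, because that is not prohibited.

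**Working it through.** **1. The plan's own figure.** Inputs: 65% response and N = 50 (SAP 9.3); Gaussian interval with continuity correction (SAP 7.2.1). Half-width = 1.96 × √(0.65 × 0.35 / N) + 1/(2N).
- N = 50: 0.1322 + 0.0100 = 0.1422, or 14.2 points. This agrees with the stated figure of about 15%.
- N = 55: 0.1261 + 0.0091 = 0.1351, or 13.5 points.

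**2. Three ways to score an excluded creatinine.** Scheduled visit days are from protocol Table 1. Platelets and LDH are taken as observed and normal, with no other qualifying visits.

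| Sequence | LOCF fills it | No measurement | Visit not met |
|---|---|---|---|
| Met 29, dialysis 43, met 57 | Responder | Responder | Non-responder |
| Met 29 and 43, dialysis across the Day 57 window | Responder | Non-responder | Non-responder |
| Met 29 only, then dialysis | Non-responder (guard) | Non-responder | Non-responder |
| Met 29, 43 and 57, then dialysis | Responder | Responder | Responder |

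**3. Main case (row 1).** Under SAP 9.4.4 the Day 43 window is Days 36 to 49 (midpoints 36 and 50, the middle day going to the later visit). Dialysis on Days 36 to 44 plus 5 days excludes every creatinine in it, and Days 29 and 57 are untouched. With LOCF, Day 43 inherits the passing Day 29 value. With no measurement, nothing in between is left to fail. Days 29 and 57 are 28 days apart and both are observed, so the guard is not engaged. Only the third column gives non-response, and no passage states that rule.

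**4. Weaker case (row 2).** The Day 57 window is Days 50 to 63; dialysis on Days 50 to 58 plus 5 days excludes all of it. LOCF then supplies Day 57 from Day 43. Because Day 43 is not the initial qualifying assessment, the literal guard does not bar it. Similarly, suppose creatinine meets its criterion on Day 57 while platelets are low, and dialysis starts by Day 71 with platelets and LDH then normal. Component-wise LOCF would make Day 71 the first qualifying visit and Day 99 the confirming one, both on the Day 57 creatinine. Both sequences need LOCF to reach excluded values.

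**5. When the text decides the result.** There are 15 post-baseline visits (Days 8 to 183), and 13 can start a run with a later confirming visit.
- Main case, run ending at the first confirming visit: responder at 13 of 13 start visits if the value is filled or ignored, 0 of 13 if the visit is scored as not met.
- Main case, response sustained to Day 183: 13 against 11. Only start Days 141 and 155 differ, because from other starts a clean 28-day run follows the dialysis.
- Weaker case, dialysis ending after the 28-day visit and response then sustained: LOCF 13, no measurement 12, not met 10. LOCF and not met differ for first-met Days 127, 141 and 155.

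These are counts of visit positions, not frequencies in patients.

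**6. Size.** If k patients are reclassified, the proportion moves by k/N: 1/50 = 2.0 points or 1/55 = 1.8 points each. The documents do not give k. For scale only, assuming N = 50 and 33 responders: k = 0 gives 66.0% (51.9 to 80.1), k = 1 gives 64.0% (49.7 to 78.3), k = 2 gives 62.0% (47.5 to 76.5).

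**The case against.** **Against the LOCF reading.** SAP 9.4.9 imputes eGFR but only excludes creatinine, which suggests that no substitute creatinine is wanted. A sample drawn and then judged unreliable is not plainly a missing assessment. SAP 5.1.1 also requires assessments obtained at least 28 days apart, and in row 2 the creatinine used at Day 57 was obtained 14 days after Day 29. The guard's evident purpose is to keep stale values from confirming. All of this stands, and it is why the confirming-visit case is secondary. It does not touch the main case, where ignoring the value also yields a responder.

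**The strict reading.** One could say that the change is not calculated under 9.4.3, so the in-between visit fails. But 9.4.3 yields wherever an imputation rule exists and points to 7.2.1.1, which contains one. SAP 5.1.1 tests measurements, and a value excluded from all analyses is most naturally not one.

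**A design choice.** Protocol 10.1 lists three criteria, none about dialysis, and dialysis status is a separate secondary endpoint. This stands in part: scoring the visit as not met is a choice, so it should be recorded and its effect shown. Neither document presents the present outcome as intended, though, and it sits badly with eGFR 10 and stage 5 at the same visit.

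**Existing safeguards.** Protocol 15.1 has medical and statistical staff settle data inclusion before lock. That is partial protection in an open-label study and supplies no scoring rule. The by-patient dialysis figure (SAP 7.2.2.1), the concomitant dialysis table (7.1.4) and the unconfirmed by-visit summaries (7.2.2.3) could reveal such patients without changing the primary proportion.

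**Conclusion.** The point holds and should be fixed. For dialysis at an in-between visit, the stated exclusion leads to a confirmed response whether the value is filled or ignored. For dialysis at the confirming visit, that result needs both LOCF on excluded values and a literal reading of the guard.

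Two stronger inferences are not supported. A reader might infer that a patient who meets the criteria once and then goes onto dialysis is counted as a responder; the guard in 7.2.1.1 closes that case, and a patient on dialysis for all 26 weeks has no baseline creatinine (SAP 9.4.2). A reader might also infer that the primary estimate is materially inflated. The documents give no count of affected patients, who must first meet all criteria, then start or resume dialysis, and have no other clean 28-day run. The number may be zero.

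What can be said is that each affected patient adds about 2 points, against a planned half-width of about 14, and that relative to scoring the visit as not met the direction is upward or nil. This assumes visits on their scheduled days and no clean unscheduled creatinine in the affected window.

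**What to change.** Add to SAP 7.2.1.1:
- A visit at which the patient is on dialysis as defined in 9.4.9 does not meet the creatinine criterion, whether as a qualifying, in-between or confirmatory visit.
- Creatinine excluded under 9.4.9 is not filled by LOCF.
- No confirmatory result may rest on a creatinine value obtained less than 28 days after the first qualifying visit.

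State there too whether LOCF applies to LDH excluded under 5.2.3 and to platelets excluded under 9.4.10, since the same question is open for both. Record the change in SAP 4.1, which now lists none, as a clarification of or departure from protocol 15.12.1. Add a sensitivity table giving the number of patients reclassified under each alternative scoring: excluded creatinine filled by LOCF, and excluded creatinine treated as no measurement.

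The cost is a few sentences, one programming change and one table. Protocol 15.1 asks for an amendment only if the primary or key secondary objectives or the study conduct change; otherwise the change is described in the clinical study report. This is a scoring rule only and leaves patient management untouched. The downside is that the response rate may be slightly less favourable and a brief dialysis episode breaks an otherwise clean run; the table shows how many patients that affects.

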8.1. Inclusion Criteria

Patients are eligible for enrollment in the study only if they meet all of the following criteria and none of the exclusion criteria:

1. Male or female patients ≥ 12 years of age and weighing ≥ 40 kg at the time of consent.
2. Evidence of TMA, including thrombocytopenia, evidence of hemolysis, and kidney injury, based on the following laboratory findings:
 - a. Platelet count < 150,000 per microliter (μL) during the Screening Period or within 28 days prior to the start of the Screening Period, **and**
 - b. LDH $\geq 1.5 \times$ upper limit of normal (ULN) during the Screening Period or within 28 days prior to the start of the Screening Period, and hemoglobin \leq lower limit of normal (LLN) for age and gender during the Screening Period or within 28 days prior to the start of the Screening Period, **and**
 - c. Serum creatinine level \geq ULN during the Screening Period in adults (≥ 18 years of age), or $\geq 97.5^{\text{th}}$ percentile for age ([Appendix A](#)) at Screening in adolescents (12 to < 18 years of age) (patients who require dialysis for acute kidney injury are also eligible).
3. Among patients with a kidney transplant:
 - a. Known history of aHUS prior to current kidney transplant, **or**
 - b. No known history of aHUS, and persistent evidence of TMA at least 4 days after modifying the immunosuppressive regimen (eg, suspending or reducing the dose) of calcineurin inhibitor ([CNI]; eg, cyclosporine, tacrolimus) or mammalian target of rapamycin inhibitor ([mTORi]; eg, sirolimus, everolimus).
4. Among patients with onset of TMA postpartum, persistent evidence of TMA for > 3 days after the day of childbirth.
5. To reduce the risk of meningococcal infection (*Neisseria meningitidis*), all patients must be vaccinated against meningococcal infections within 3 years prior to, or at the time of,

initiating study drug. Patients who receive a meningococcal vaccine less than 2 weeks before initiating ALXN1210 treatment must receive treatment with appropriate prophylactic antibiotics until 2 weeks after vaccination. Patients who have not been vaccinated prior to initiating ALXN1210 treatment should receive prophylactic antibiotics prior to and for at least 2 weeks after meningococcal vaccination.

6. Patients < 18 years of age must have been vaccinated against *Haemophilus influenzae* type b (Hib) and *Streptococcus pneumoniae* according to national and local vaccination schedule guidelines.

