7.2.2.5. CKD Stage

CKD stage will be summarized over time by presenting the number and proportion of patients that improved (excluding those with Stage 1 at baseline as they cannot improve), worsened (excluding those with Stage 5 at baseline as they cannot worsen), and stayed the same compared to CKD stage at baseline. Stage 5 will be considered the worst category, while stage 1 will be considered the best category (see [Section 9.4.11](#) for details). A 2-sided 95% CI for each proportion will be provided. The CIs will be based on exact confidence limits using the Clopper-Pearson method. This summary will be repeated by the kidney transplant status at enrollment.

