9.4.2. Definition of Baseline Values

For the analysis, the baseline value is defined as the average of the values from the assessments performed prior to the first study drug infusion (these can include results from Screening and the Day 1 visit).

When a patient is on dialysis at baseline, then the first valid creatinine value to be used as the baseline value will be the first assessment ≥ 6 days post-dialysis. If a patient is on dialysis during the entire 26 week Initial Evaluation Period, then the baseline creatinine will not be calculated.

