9.4.11. Assignment of CKD Stage

Chronic kidney disease (CKD) stage will be classified based on the National Kidney Foundation Chronic Kidney Disease Stage as follows:

Table 6: Stages of Chronic Kidney Disease

Stage	Description	eGFR (mL/min/1.73 m ²)
1	Normal or High	≥90
2	Mildly Decreased	60-89
3a	Mildly to Moderately Decreased	45-59
3b	Moderately to Severely Decreased	30-45
4	Severely Decreased	15-29
5	Kidney failure	< 15 (or dialysis)

Note: In the absence of evidence of kidney damage, neither stage 1 nor 2 fulfill the criteria for CKD
 Source: [KDIGO 2012 Clinical Practice Guideline for the Evaluation and Management of Chronic Kidney Disease](#). 2013. 3: 19-62.

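### A fixed on-dialysis eGFR of 10 scores starting dialysis as a gain for patients whose baseline is below 10, and the CKD-stage table scores it as no change for every Stage 5 entrant

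*SAP*

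**What the plan says.** **eGFR on dialysis.** SAP 9.4.9 states that "all serum creatinine values obtained while a patient is on dialysis will be excluded from all analyses" and that eGFR "will be imputed with a value of 10" during that time. The period is defined there too: "A patient will be considered on dialysis from the first day of dialysis through 5 days after the end of dialysis". Protocol 15.8.2.4 says only that a value will be imputed, so the figure 10 is the SAP's choice. The SAP gives no reason for it, no cap and no sensitivity analysis of it.

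**Baseline and change.** In SAP 9.4.2, "the baseline value is defined as the average of the values from the assessments performed prior to the first study drug infusion". SAP 9.4.3 gives the arithmetic: "Change from baseline will be calculated as the baseline value subtracted from the value at a particular time point".

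**Who can enter.** The adult renal criterion (Protocol 8.1, criterion 2c) asks for serum creatinine at or above "ULN during the Screening Period in adults". It sets no upper limit, and no criterion sets an eGFR floor. Exclusion 18 removes only chronic dialysis for end-stage disease.

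**CKD stage.** SAP Table 6 defines Stage 5 as "< 15 (or dialysis". SAP 7.2.2.5 reports patients who "worsened (excluding those with Stage 5 at baseline as they cannot worsen". Protocol 15.8.2.5 and the synopsis carry the same exclusion.

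**Dialysis status.** SAP 7.2.2.1 tabulates dialysis requirement over time for patients on dialysis at baseline, for those not on it, and overall. It uses exact intervals and adds a by-patient figure.

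**The concern.** Starting dialysis is a loss of renal function. For a patient already below 10, a flat imputed value of 10 turns that loss into a numerical gain, which then enters the eGFR summaries and the repeated-measures model of SAP 7.2.2.4.

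The CKD-stage table does not offset this. The stated reason for leaving Stage 5 entrants out of the worsened category is true of the stage scale but not of the patients, because one who is off dialysis can still go on to it. That event is recorded as no change. The reverse is also hidden: a patient who stops dialysis with eGFR still below 15 is not counted as improved.

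New dialysis on study is foreseen, since Protocol 9.7 sets conditions for it after the first dose. At stake is whether these two renal endpoints describe the patients with the least remaining function correctly.

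**Working it through.** The plan gives no figure for the effect of this rule, so there is none to reproduce. The inputs are the imputed value of 10 (SAP 9.4.9), change = visit value - baseline (SAP 9.4.3), the stage limits (SAP Table 6) and N = 55 (SAP 9.3).

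**Step 1: score when dialysis starts.** For off-dialysis baseline b, change = 10 - b. The last column applies the lower of 10 and the last off-dialysis eGFR, taking that last value to equal b.

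| Baseline b | Stage at entry | Change as planned | Stage on dialysis | Change with cap |
|---|---|---|---|---|
| 4 | 5 | +6 | 5 | 0 |
| 6 | 5 | +4 | 5 | 0 |
| 8 | 5 | +2 | 5 | 0 |
| 10 | 5 | 0 | 5 | 0 |
| 12 | 5 | -2 | 5 | -2 |
| 14 | 5 | -4 | 5 | -4 |
| 15 | 4 | -5 | 5 | -5 |
| 29 | 4 | -19 | 5 | -19 |

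The change is positive only for b < 10. For b from 10 to just under 15 it is 0 to about -5, which is not an improvement.

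**Step 2: CKD stage.** Every Stage 5 entrant remains at Stage 5 on dialysis, falls under unchanged, and is outside the worsened category by rule. A Stage 4 entrant who starts dialysis moves to Stage 5 and counts as worsened. The stage problem is therefore confined to Stage 5 entrants.

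**Step 3: effect on the mean.** Suppose k patients with baseline b below 10 are on dialysis at a visit where all 55 contribute. Compared with scoring them at zero change, the mean is shifted by k × (10 - b) / 55. The values of k and b are assumptions.

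- k = 1, b = 8: 2/55 = +0.04
- k = 1, b = 4: 6/55 = +0.11
- k = 3, b = 6: 12/55 = +0.22
- k = 5, b = 8: 10/55 = +0.18
- k = 5, b = 4: 30/55 = +0.55

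**Step 4: stage boundaries.** SAP Table 6 gives Stage 3a as 45-59 and Stage 3b as 30-45, so an eGFR of 45 belongs to both. Protocol Appendix J ends Stage 3b at 44.

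**The case against.** The best defence is that progression to dialysis has its own endpoint. Dialysis requirement status is the first-listed secondary endpoint, and the SAP extends it beyond the protocol's analysis (15.8.2.1) to patients not on dialysis at baseline. A reader might infer that new dialysis goes unreported; SAP 7.2.2.1 shows that it does not. What remains is that this table is not split by baseline CKD stage and does not alter the eGFR or CKD-stage results.

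Other stronger readings are also unsupported:

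- **That both endpoints misread every Stage 5 entrant.** The eGFR sign error needs a baseline below 10. From 10 to just under 15, only the stage table hides the event.
- **That a patient on dialysis at baseline who comes off with eGFR 8 is scored -2.** This holds only if baseline eGFR is the imputed 10. SAP 9.4.2 takes baseline creatinine for such patients from the first assessment at least 6 days after dialysis and does not say whether eGFR follows. If it does, and that assessment gives the 8, the score is 0.
- **That the main result is at risk.** The primary endpoint uses platelets, LDH and creatinine, so the imputed 10 never enters it. SAP 7.2.1.4 describes an estimation study without formal tests.
- **That the worsening rate rests on a known small denominator.** The documents do not give the share entering at Stage 5, and those on dialysis at entry could not newly start it anyway.

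It is also fair to say that the Stage 5 exclusion is correct on the prespecified scale and stands in the protocol. That argues for adding information to the table rather than redefining the stages.

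**Conclusion.** The point holds in limited form. The SAP's rules score a dialysis start as an eGFR gain when the off-dialysis baseline is below 10, and as no change in CKD stage for any Stage 5 entrant off dialysis. Both follow directly from the text, and nothing in the eligibility criteria rules such patients out.

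The effect on mean eGFR change is probably small: about +0.04 to +0.55 mL/min/1.73 m² for 1 to 5 affected patients of 55 with baselines of 8 to 4. Those counts and baselines are assumed, because the documents give neither. The stage-table problem does not depend on them. The overlap at eGFR 45 is a separate, minor error that affects only a value of exactly 45. The correction is worth making because the score runs in the wrong direction and the repair is cheap.

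**What to change.** 1. **SAP 9.4.9.** For a patient who starts dialysis after baseline, set eGFR on dialysis to the lower of 10 and the last off-dialysis eGFR before that episode. Keep 10 for patients on dialysis at baseline, and state whether their baseline eGFR is the imputed 10 or follows the post-dialysis creatinine rule in SAP 9.4.2. The cap uses only earlier data and ensures that going on to dialysis never raises the value. A patient whose eGFR had already risen, say from 6 to 8, would still show +2, but that gain was measured before dialysis.
2. **SAP 7.2.2.5.** Keep the prespecified stage table. Add rows for baseline Stage 5 patients giving the number off dialysis who start it and the number on dialysis who stop, with Clopper-Pearson intervals. List the addition in SAP 4.1, which now reports no changes from the protocol.
3. **SAP Table 6.** Change Stage 3b from 30-45 to 30-44, to match Protocol Appendix J.

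The cost is SAP wording and a little programming on data already collected. The reported eGFR change may be slightly less favourable. The added rows leave the objectives and conduct unchanged, so on the terms of Protocol 15.1 they should not need a protocol amendment.
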